11 RISK ANALYSIS

Shoulder surgery in the BCP is routinely used in clinical practice. Participants who agree to be part of the trial will experience no additional risks above those normally associated with this routine procedure. X-ray imaging is performed for some surgical procedures as the normal course of intraoperative patient care. Suspected adverse neurological outcomes associated with the surgery may require further imaging in the form of cerebral CT / MRI as is standard practice. Such imaging would be unrelated to the monitoring of cerebral oximetry.

If a participant is found to be experiencing psychological distress (i.e. depression, anxiety or suicidality) or is found to have a significant cognitive impairment, the following procedures will be put in place. Psychological distress will be monitored initially through the psychological measures being used and will be administered by a clinical psychology trainee or other health professional. These measures are standardised and have recognised clinical cut-off criteria. The medical consultant in the project team will be informed of anyone meeting the criteria for at least mild to moderate levels of distress. As the medical consultant is responsible for the care of all patients, he will take responsibility for any onward referral or medical management as per standard clinical practice. A similar procedure will be followed in the case of significant cognitive impairment. The neuropsychological tests are standardised with norms provided to indicate possible impairment. The medical consultant will be informed of anyone meeting the criteria for mild to moderate impairment and this will be managed as per standard clinical practice with referral for further assessment. Additionally, any mood- or cognitive-related concerns raised by participants will be brought to the attention of the medical consultant.

12 BUDGET AND FUNDING IN-KIND SUPPORT

	Item	Source	Details	Costs to BHULRI & UQ
1	Investigator time & Research assistant	BHULRI & UQ	Protocol development, ethics, study assessments, participant follow-up, data entry, analysis, writing paper for publication, submission.	In Kind
2	INVOS™ monitors/sensors	Supplier	Standard monitors/sensors used at Brisbane Private Hospital for this population	Nil
3	FORE-SIGHT® monitors/sensors	Supplier	Sufficient monitors/sensors to be provided for purpose of research	Nil

13 DISSEMINATION

Findings from this investigation will be disseminated locally through existing state and nation wide clinical networks and in-service education amongst relevant clinical teams (e.g. multi-disciplinary upper limb teams in hospital facilities).

Research outcomes will also be disseminated widely through peer-reviewed publications as well as through local, national and/or international conferences. The proposed dissemination of these findings is likely to guide models of healthcare both nationally and internationally.

14 CLINICAL INVESTIGATION PLAN SUMMARY- PART TWO

TITLE	Health professionals' experiences of post-operative cognitive decline
INVESTIGATORS	Principal: Associate [name], [name], [name], [name] Associate: [name], [name], [name], [name], [name]
OBJECTIVES	The general aim of the study is to understand what professionals experience and understand of POCD, and/or what they might expect to experience.
STUDY DESIGN	Descriptive Survey
SITES	Brisbane Private Hospital
NUMBER OF SUBJECTS	Approximately 200 participants will be recruited to this study.
TARGET POPULATION	Participants will be currently practicing medical, nursing and allied health practitioners.
LENGTH OF CLINICAL INVESTIGATION	It is anticipated that this study will require 6 months from commencement.
OUTCOME	Demographic data and outcome variables will be examined using descriptive statistics (means, standard deviations [SDs], and percentages). Factors examined will be: 
 • Whether each individual clinician has encountered POCD in practice • What cognitive functions were affected or what they would expect to see • The duration seen or expected • Whether there were any emotional symptoms or whether they would expect emotional symptoms • How it was managed or how they would expect it to be managed • What else could be done to manage POCD

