15.1 LAYMAN'S SUMMARY

As there is no existing literature base, it would be invaluable to examine POCD from a clinicians perspective, particularly surrounding the duration, current prevention techniques and management in a clinical setting.

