18 OUTCOME MEASURES

18.1 SURVEY

A survey has been designed and developed on Qualtrics to examine each individual clinician's experiences of POCD in practice (24.6). The participant information sheet and consent form will be provided online at the beginning of the survey (24.7 & 24.8). The questions will identify whether each individual clinician has encountered POCD or not in practice. If they have encountered POCD in clinical practice follow up examination includes how many times they have encountered POCD, what cognitive functions were effected, the duration of POCD, were there any emotional symptoms, how it was managed and what else could have been done to manage POCD. If they have not previously encountered POCD in clinical practice follow up examination includes what cognitive functions they expect to be effected, would they expect emotional symptoms and how they might manage a patient experiencing POCD. The survey is expected to take 10 minutes to complete.

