24.6 Participant Survey – STUDY TWO

HEALTH PROFESSIONALS' EXPERIENCES OF POST OPERATIVE COGNITIVE DECLINE

PROFESSIONAL BACKGROUND

The following questions are about you and your profession.

Age: _____

Gender:

Male

Female

State:

Queensland

New South Wales

Victoria

South Australia

Canberra

Western Australia

Tasmania

Other:

What is your profession?

Medical

Area: _____

Nursing

Psychology

Neuropsychology

Occupational Therapy

Speech Pathology

Physiotherapy

Other

What level are you currently in your profession? _____ (e.g. interns, registrar, fellow, professor)

How senior is your position in your current organization:

Very senior

Senior

Intermediate

Junior

Very junior

How many years have you been in clinical practice (years)?

≤1

1-3

4-7

8-10

≥10

How long have you worked for your *current* organisation? _____ (weeks/months/years)

Who is your employer?

- Public Sector
- Private Sector
- Private Practice
- University
- Multiple

What population(s) do you currently work with?

- Paediatric
- Adult
- Geriatric

In which areas (e.g. surgical, neurology, internal medicine, allied health): _____

Postoperative cognitive dysfunction (POCD) is a decline in cognitive function more typically seen after a few days to several months following surgery, but can last for several years.. It is distinct from delirium, which only occurs within the first few days. The decline in cognitive function is not attributed to any adverse complications and occurs peri-operatively. What we would like to know is your experiences of POCD in a *clinical setting*.

1. Have you encountered POCD before?

- YES
- NO

If you answered yes please complete questions 2 to 9. If you answered no please go to question 10.

2. How many times have you encountered it? _____ (number)

3. What cognitive functions were impacted? If you have seen more than one case of POCD, identify all the areas that were affected across the people you have seen:

- Short Term Memory
- Long Term Memory
- Attention/ Working Memory
- Planning/Organisation
- Inhibition
- Initiation
- Self-monitoring
- Emotional Control
- Gross and Fine Motor Control
- Language
- Learning

4. For the problems you identified, please number them in order of the general impact you felt this had on the person's (or people, if you have encountered more than one case) everyday functioning from 1= least impactful to 5 = most impactful.

- Short Term Memory
- Long Term Memory
- Attention/ Working Memory

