- Planning/Organisation
- Inhibition
- Initiation
- Self-monitoring
- Emotional Control

- Gross and Fine Motor Control
- Language
- Learning
- 5. How long did the POCD last?
- 3-7 days
- 8-28 days
- 4-6 weeks
- 6 weeks to 3 months
- >3 months
- >12 months
- Unknown

6. Did people experience any associated emotional changes? Please tick all that apply

- Low mood
- Nervousness/Worry
- Panic
- Stress
- Fatigue
- Change in sleep
- Irritability
- Weight gain/loss
- Change in appetite
- Excessive crying
- Poor concentration
- Restlessness
- None

7. How was the POCD and/or emotional changes managed?

- No additional intervention to treatment-as-usual
- It was monitored
- Assessment
 - Brief screen (e.g. MMSE)
 - Full Cognitive Battery
- Referral
 - Clinical Psychologist
 - Neuropsychologist
 - Speech Therapist
 - Occupational Therapist
 - Neurologist
 - Other professional
- Other: _____

8. In your opinion could anything else have been done to manage the cognitive and/or mood symptoms? _____

9. If you have any additional information you would like to share about POCD or to provide comments on the survey, please do so here. _____

10. Given the nature of POCD as described above, what cognitive functions do you feel might be vulnerable? Please rank these in order from the 1=most likely to 5= least likely:

- Short Term Memory
- Long Term Memory
- Attention/ Working Memory
- Planning/Organisation
- Inhibition
- Initiation
- Self-monitoring
- Emotional Control
- Gross and Fine Motor Control
- Language
- Learning

11. Would you anticipate changes to emotional functioning? If so, what might you expect to see? Please rank these in order from the 1=most likely to 5= least likely

- Low mood
- Nervousness/Worry
- Panic
- Stress
- Fatigue
- Change in sleep
- Irritability
- Weight gain/loss
- Change in appetite
- Excessive crying
- Poor concentration
- Restlessness
- None

12. In your opinion, how do you feel POCD should be managed?

- No additional intervention to treatment-as-usual
 - Monitor the POCD
 - Provide Assessment
 - Brief screen (e.g. MMSE)
 - Full Cognitive Battery
 - Further Referral
 - Clinical Psychologist
 - Neuropsychologist
 - Speech Therapist
 - Occupational Therapist
 - Neurologist
 - Other professional
- Other: _____

9. Any other comments _____

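### Study Two lists expected duration of POCD as an outcome, but the survey never asks for it; the duration bands for cases seen also overlap

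*Protocol*

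**What the plan says.** The objective of Study Two in section 14 is to "understand what professionals experience and understand of POCD, and/or what they might expect to experience", so it covers both experience and expectation. The outcome list in the same section includes "The duration seen or expected". The layman's summary (section 15.1) says that the clinician's view is of value "particularly surrounding the duration, current prevention techniques and management in a clinical setting".

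The survey in section 24.6 splits respondents at question 1, on whether they have encountered POCD: "If you answered yes please complete questions 2 to 9. If you answered no please go to question 10". Question 5, in the yes branch, asks "How long did the POCD last" and offers seven options: 3-7 days, 8-28 days, 4-6 weeks, 6 weeks to 3 months, >3 months, >12 months and unknown.

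In the no branch, question 10 asks "what cognitive functions do you feel might be vulnerable", question 11 asks "Would you anticipate changes to emotional functioning? If so, what might you expect to see", and question 12 asks how POCD should be managed. A comments box follows.

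Section 18.1 describes the same two branches. It includes duration for clinicians who have met POCD. For the others it begins "If they have not previously encountered POCD in clinical practice follow up examination includes what cognitive functions they expect to be effected" and goes on to emotional symptoms and management, without duration.

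**The concern.** Section 14 promises duration from both groups of clinicians, while the instrument collects it from one. An analysis plan cannot recover an answer that was never requested, so this has to be settled in the survey or in the outcome list. If it is left, part of a listed outcome will have no data, on a topic that the Study Two introduction and layman's summary both stress.

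The second issue is the response scale of question 5. Where options overlap, two clinicians describing the same duration can correctly tick different boxes. This matters most at the long end, where the two top options appear intended to separate cases lasting beyond a year from shorter ones.

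**Working it through.** No sample size, power or error rate is involved: section 15.9 states that no power analysis applies, and section 20.1 plans descriptive statistics only. The check is a trace of the routing and a conversion of the bands to days.

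**1. Does each paired factor in section 14 have an item in both branches of section 24.6?**

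| Factor in section 14 | Yes branch | No branch |
|---|---|---|
| Cognitive functions, seen or expected | Question 3 | Question 10 |
| Duration, seen or expected | Question 5 | None |
| Emotional symptoms, seen or expected | Question 6 | Question 11 |
| Management, actual or expected | Question 7 | Question 12 |

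Duration is the only paired factor without a no-branch item. Of the three structured no-branch questions (10, 11 and 12), 0 of 3 ask about duration. Section 18.1 gives the same result: duration appears for those who have met POCD and not for the others. Two separate parts of the protocol agree with each other and differ from section 14, so a passage lost in text extraction is not a likely explanation.

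**2. Do the question 5 bands exclude one another?** Using 4 weeks = 4 × 7 = 28 days and 6 weeks = 6 × 7 = 42 days:

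| Option | Range | Overlap |
|---|---|---|
| 3-7 days | 3 to 7 days | None |
| 8-28 days | 8 to 28 days | Day 28, with the next band |
| 4-6 weeks | 28 to 42 days | Day 28 with the band above, day 42 with the band below |
| 6 weeks to 3 months | 42 days to 3 months | Day 42, with the band above |
| >3 months | Over 3 months, no upper limit | Contains all of >12 months |
| >12 months | Over 12 months | Wholly inside >3 months |

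There are three overlaps. Two are ties at a single point (28 days and 6 weeks). The third is full nesting: every duration over 12 months also satisfies >3 months. The count in >3 months is therefore the 3-to-12-month cases plus an unknown number of longer ones. The sum of the two options is a valid count for over 3 months, provided that each respondent ticks only one.

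**3. Does question 5 allow for several cases?** Question 2 records how many times POCD was encountered. Questions 3 and 4 tell respondents how to answer if they have seen more than one case, and question 6 invites all that apply. Question 5 gives no instruction.

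**The case against.** The strongest reply is that the inconsistency amounts to two words in a summary table. Section 18.1 and the questionnaire agree that duration is asked only of those who have met POCD, and deleting the words on expectation from section 14 would reconcile the text. None of the five research questions in section 15.5 names duration, and the layman's summary frames it in a clinical setting, which question 5 serves. This stands, and it keeps the point small. It does not remove the contradiction, because the outcome list and the stated objective still cover expectation.

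Adding an item also has a weakness. Before question 1, the survey tells every respondent how long POCD typically lasts and that it can last for years. Clinicians with no experience of it may simply return that information, so a new item would be worth less than it first appears.

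Three stronger readings are tempting and are not supported:

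- *That the duration outcome as a whole cannot be reported.* The seen half is collected, and percentages can be given as section 20.1 plans. The overlaps do not prevent this.
- *That a planned comparison of seen with expected duration is lost.* No such comparison is planned. The one comparative research question, 15.5(v), concerns professions and clinical populations.
- *That question 5 forces a single duration on respondents with many cases.* The printed text does not show whether the online item accepts one answer or several. The fair criticism is that it is silent.

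**Conclusion.** The point holds in a limited form. Expected duration is missing for every clinician who has not encountered POCD, whatever the size of that group. The protocol gives no basis for estimating what share of the roughly 200 respondents that will be, so no head count is offered. These respondents still supply encounter status, cognitive functions, emotional symptoms and management.

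The band overlap is a lesser defect. It makes the split at 12 months unreadable and leaves ties at 28 days and 6 weeks, but the total over 3 months remains usable. That last statement assumes one answer per respondent.

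Both defects are minor. They concern a stand-alone descriptive survey and do not touch Study One, its primary outcome or its participants. The conclusion assumes that the live survey matches section 24.6.

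**What to change.** The protocol does not say whether the survey has launched, so the remedy depends on that.

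**If it has not launched:**
- Add one item to the no branch asking how long the respondent would expect POCD to last, and add duration to the matching list in section 18.1. Acknowledge that the preamble on duration may prime the answers, and consider where each is placed.
- Use exclusive bands in both branches: 3-7 days; 8-28 days; 29 days to 6 weeks; >6 weeks to 3 months; >3 to 12 months; >12 months; unknown.
- State in question 5 how a respondent with several cases should answer. Which rule to use is for the investigators to choose.

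If the investigators do not want the expected half, deleting it from section 14 also resolves the contradiction, and only the changes to question 5 remain.

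**If data collection has begun:** delete the expected half of the outcome from section 14, leave the bands as they are so that the data set is not split between two scales, and report >3 months and >12 months combined.

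The cost before launch is one online item, relabelled options and a few seconds per respondent. After launch it is a text amendment and one reporting rule, with the loss of the expected half and of the split at 12 months.

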15 INTRODUCTION

There are no published studies on the experiences of POCD from a health professionals' perspective. With so many debates surrounding the nature and duration of POCD in the literature (e.g. Berger et al., 2015), an understanding of experiences and expectations from the treating clinician's perspectives would be an important supplement to the current research base. As a result the nature, duration, prevention techniques and management of POCD from a practicing clinicians' perspective particularly, require further investigation. Further research in these areas indicated and the proposed study aims to address the issues raised here.

15.1 LAYMAN'S SUMMARY

As there is no existing literature base, it would be invaluable to examine POCD from a clinicians perspective, particularly surrounding the duration, current prevention techniques and management in a clinical setting.

15.2 PURPOSE OF THE INVESTIGATION

The purpose of this investigation is to gain clinicians' perspectives regarding the experience of POCD in Australian practice. Currently, there is no existing literature base to suggest what clinicians encounter day to day in clinical practice and what is actually being done to manage POCD and possible psychological sequela. A clinician's perspective would provide practical implications for the clinical stakeholders and their patients as well as for the management of POCD and potential for services.

15.3 INTERVENTION GROUPS

The study will involve a descriptive survey. Clinicians who meet eligibility criteria will be able to complete the survey.

15.4 GENERAL AIM OF THE STUDY

The general aim of the study is to understand what professionals experience and understand of POCD, and/or what they might expect to experience.

15.5 RESEARCH QUESTIONS

STUDY TWO has five research questions, based on the perspective of practicing clinicians;

- (i) How many times has POCD been seen in a clinical setting?
- (ii) How often are psychological symptoms seen comorbidly with POCD?
- (iii) How POCD is currently managed in clinical practice?
- (iv) What are clinician perspectives on how POCD should be managed?
- (v) Does the experience of POCD differ between professions and clinical populations?

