15.9 SAMPLE SIZE

As this is a descriptive study examining practicing clinicians perspectives of POCD no power analyses can be conducted.

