20.1 STATISTICAL METHODS

As this is a descriptive study, demographic data and outcome variables will be examined using descriptive statistics (means, standard deviations [SDs], and percentages).

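### Study Two asks how often psychological symptoms accompany POCD, but survey question 6 records only whether a clinician ever saw each symptom

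*Protocol*

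**What the plan says.** Protocol 15.5 lists five research questions for Study Two, put from the practising clinician's point of view. Question (ii) is "How often are psychological symptoms seen comorbidly with POCD". Question (v) asks whether the experience of POCD differs between professions and clinical populations.

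The summary in section 14 words the corresponding outcome differently: "Whether there were any emotional symptoms or whether they would expect emotional symptoms". Section 18.1 describes the survey in the same any-or-none terms.

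In the survey (24.6), clinicians who have encountered POCD answer three relevant items:
- Question 2, "How many times have you encountered it", takes one number.
- Question 3, on cognitive functions, carries an explicit pooling instruction: "If you have seen more than one case of POCD, identify all the areas that were affected across the people you have seen".
- Question 6, "Did people experience any associated emotional changes? Please tick all that apply", offers 12 symptoms and 'None'. It is answered once per clinician and has no field for a count or proportion.

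Section 20.1 plans that "demographic data and outcome variables will be examined using descriptive statistics (means, standard deviations [SDs], and percentages" are reported. The target is about 200 clinicians (section 14: "Approximately 200 participants will be recruited to this study"). Section 15.9 states that "no power analyses can be conducted", so there is no sample-size figure to check.

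**The concern.** A question that begins with *how often* needs a numerator and a denominator. The survey collects the denominator (cases seen) but, for a clinician with several cases, not the numerator (cases with symptoms). A clinician who saw low mood in 1 of 20 cases and one who saw it in all 20 give the same answers to questions 2 and 6.

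Two things are at stake. First, the percentage that the plan yields is the share of clinicians who ever saw a symptom, which is a different quantity from the one question (ii) asks for. Second, the chance of ever having seen a symptom grows with the number of cases seen. Under question (v), a profession with larger caseloads would therefore report more symptoms even if the per-case frequency were the same everywhere.

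The gap lies in the data collection form. A separate analysis plan could not restore a count that was never asked for.

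**Working it through.** **1. Question against instrument.**

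| Place | What is asked or measured |
|---|---|
| 15.5, question (ii) | How often symptoms accompany POCD |
| 14 and 18.1 | Whether there were any emotional symptoms |
| 24.6, question 2 | Number of POCD cases, one number per clinician |
| 24.6, question 6 | Symptoms ticked once per clinician, about people in the plural |
| 20.1 | Means, SDs and percentages |

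Question 6 agrees with sections 14 and 18.1. It does not agree with 15.5 (ii). The pooling over cases is stated outright only in question 3; in question 6 it is inferred from the plural wording and the single answer.

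**2. What a response tells us.** Let m be the answer to question 2.
- m = 1: the tick list describes that one case, so the case-level answer is exact.
- 'None' ticked: the number of affected cases is 0 for any m.
- m > 1 and a symptom ticked: the number of affected cases lies anywhere from 1 to m, so the clinician's proportion lies between 1/m and 1. That is 0.50 to 1 for m = 2, 0.20 to 1 for m = 5, 0.10 to 1 for m = 10 and 0.05 to 1 for m = 20.

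The first two groups should not simply be pooled to estimate a rate. That would keep the clinicians with several cases who saw nothing and drop those who saw something, which biases the estimate downwards.

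**3. How the reported percentage moves with caseload.** The protocol gives neither a per-case symptom rate p nor a caseload distribution, so both are assumed here. If cases are independent with a common p, then

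P(symptom ticked) = 1 − (1 − p)^m

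| Assumed p | m = 1 | m = 5 | m = 10 | m = 20 |
|---|---|---|---|---|
| 10% | 10% | 41% | 65% | 88% |
| 20% | 20% | 67% | 89% | 99% |
| 30% | 30% | 83% | 97% | 99.9% |

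For example, with p = 20% and m = 5: 1 − 0.8^5 = 1 − 0.328 = 0.672.

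**4. The same relation in reverse.** Suppose 80% of clinicians tick a symptom and all have the same caseload. Then p = 1 − 0.2^(1/m), which is 80% for m = 1, 28% for m = 5, 15% for m = 10 and 8% for m = 20. One reported percentage is compatible with very different per-case frequencies.

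**5. Question (v).** Take two professions with the same p = 20%, one whose members have each seen 1 case and one whose members have each seen 5. The planned percentages would be 20% and 67%, a difference due to caseload alone.

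**The case against.** The strongest defence is that the instrument measures what section 14 defines. The outcome there is whether there were any emotional symptoms, 18.1 repeats it, and the general aim in 15.4 concerns what professionals experience and understand. On that view, question (ii) is loosely worded and asks how commonly clinicians report having seen such symptoms. This stands in part: it shows that the outcome and the survey agree with each other, and it makes rewording (ii) a legitimate remedy. It does not make the survey answer (ii) as written. The neighbouring question (i) asks for a number of times and is answered by a count; (ii) has neither a count nor a frequency category.

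A reader might infer that no frequency at all can be estimated. The documents do not support that. Clinicians with one case and those who tick 'None' give case-level information, the others give bounds, and the share of clinicians who ever saw a symptom is fully estimable. A rate could also be modelled from questions 2 and 6 together under strong assumptions of independence and a common rate, though the protocol plans no such model.

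A reader might also infer a fixed overstatement of about fivefold. That is only 0.99/0.20, for one assumed rate and 20 cases per clinician. At 20 cases the ratio is about 8.8 for a 10% rate (0.878/0.10) and 3.3 for a 30% rate (0.999/0.30), and with one case per clinician it is 1.

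Nor does 20.1 say that the percentages will be presented as case rates; misreading them so is a risk, not something the plan states. On (v), it is fair to reply that a profession with more cases does have a different experience of POCD, and that results can be tabulated by question 2. That helps, but the plan does not provide for it.

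**Conclusion.** The point holds in a limited form. Research question (ii) asks for a frequency, while question 6 yields an ever-seen indicator per clinician. The per-case frequency cannot be obtained from clinicians who have seen more than one case and tick a symptom, and the planned percentages rise with caseload, which carries over to comparisons under (v).

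The size cannot be fixed from the documents. The range in the working (for 10 cases per clinician, 65% to 97% ticking at assumed rates of 10% to 30%) rests on independent cases with a common rate and on invented caseloads. If nearly all respondents have seen only one case, the problem largely disappears; the protocol does not say how likely that is.

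Severity is minor. Study Two is a descriptive, low-risk survey without hypotheses, and nothing here touches Study One.

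**What to change.** Either of two changes resolves the mismatch.

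1. **Add one numeric item after question 6**, for example: *Of the cases counted in question 2, in how many did you see any emotional change?* Summarise (ii) as the distribution of the per-clinician proportions. A pooled ratio of affected to total cases is less suitable: recruitment is from one hospital and its associated email lists (15.8), so clinicians may count the same patients, and respondents who recall large caseloads would dominate. Keep the tick list to describe the type of symptom. Under (v), compare professions on the per-clinician proportion or within bands of question 2.

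2. **Reword question (ii)** to the proportion of POCD-experienced clinicians who have observed such symptoms, in line with section 14, and report it by caseload from question 2. This needs no new item and is the only route for responses already collected.

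The cost is one field in an online questionnaire, or one sentence in the protocol. The downsides of the first option are that the count relies on recall, as question 2 already does, and that it covers any emotional change, so the frequency of each single symptom remains unknown.
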